## **9.0 RECORDS TO BE KEPT**

At time of registration – Patient consent form, signed eligibility checklist and registration card.

Following breast conservation surgery for the second time, prior to beginning breast re-radiation, the cosmetic results of breast conservation will be assessed. Appendix I should be used. The same will be used to reassess the patient during radiation therapy, at one month post-radiation therapy, and every three months thereafter for one year, followed bi-annually for the remainder of the 5 year follow-up.

Follow-up Form - at time of disease response assessment, every three months during the first year and every 6 months thereafter for 5 years.

## **10.0 PATIENT CONSENT AND PEER JUDGEMENT**

All institutional, NCI, FDA, State and Federal regulations concerning informed consent and peer judgement will be fulfilled. Typically, patients choosing to participate in this trial will be consented either at the time of consultation with, or shortly after their meeting with the radiation oncologist. As the referral to the radiation oncologist can come at varying stages in the diagnostic/treatment process (i.e. right after biopsy, but before lumpectomy, or after lumpectomy and before chemotherapy etc...), his/her participation in our Multidisciplinary Tumor Board is paramount. It is at these weekly meetings that treatment recommendations are formulated—if a patient is scheduled to have a lumpectomy and her case is presented at tumor board, then the radiation oncologist may then see the patient right before surgery and assess interest in the study prior to surgery. That said, even if a patient has already had a lumpectomy with negative

margins, she may always be taken back to the operating room if she decides to be in this trial and if it is deemed that to perform the radiation, she needs to be taken to the OR (i.e. for IORT, or for MammoSite placement).

## APPENDIX I

### COSMETIC GUIDELINES

**Patient #:** \_\_\_\_\_

Following breast conservation surgery, prior to beginning breast re-radiation, the cosmetic results of breast conservation will be assessed using these guidelines. The same guidelines will be used to reassess the patient during radiation therapy, at one month post-radiation therapy, and every three months thereafter for one year, then biannually for a total of 5 years.

Circle the number next to the word that best describes the cosmetic result.

1. EXCELLENT: When compared to the untreated breast or the original appearance of the treated breast, there is minimal or no difference in the size or shape of the treated breast. The way the breast feels (its texture) is the same or slightly different. There may be thickening, scar tissue, or fluid accumulation within the breast but not enough to change the appearance.
2. GOOD: There is mild asymmetry between the breasts, which means that there is some acceptable difference in the size or shape of the treated breast as compared to the opposite breast or the appearance of the breast before treatment. There may be some mild reddening or darkening of the breast. The thickening or scar tissue within the breast causes a mild change in its shape or size.
3. FAIR: Moderate deformity of the breast, with an obvious difference in the shape and size of the treated breast. This change involves  $\frac{1}{4}$  or less of the breast. There can be moderate thickening or scar tissue of the skin and the breast, and there may be obvious color changes.
4. POOR: Marked change in the appearance of the treated breast involving more than  $\frac{1}{4}$  of the breast tissue. The skin change may be obvious and detract from the appearance. Severe scarring and thickening of the breast, which clearly alters its appearance may be present. In retrospect, the breast may have been better treated by a mastectomy.

Code a response for each of the following items:

1. None
2. Yes, seen on close observation
3. Yes, seen on casual observation

\_\_\_\_\_ skin telangiectasia

\_\_\_\_\_ skin atrophy

\_\_\_\_\_ hyperpigmentation

\_\_\_\_\_ erythema

\_\_\_\_\_ fibrosis

\_\_\_\_\_ skin dimpling or indentation

\_\_\_\_\_ other significant treatment effects

specify: \_\_\_\_\_

During radiation therapy the patient will be evaluated weekly by the radiation oncologist. The following scale will be used to classify the acute skin reactions during treatment:

1. no change noted
2. faint erythema
3. bright erythema
4. dry desquamation with or without erythema
5. small to moderate area of moist desquamation
6. large area of moist desquamation
7. ulceration, hemorrhage, or necrosis

Signature of person completing the form: \_\_\_\_\_

Date: \_\_\_\_\_

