## SCHEMA

Excisional Biopsy Followed by Partial Breast Irradiation for patients with ipsilateral breast tumor recurrence who were first treated with breast conserving surgery and whole breast radiation therapy.

1. Intraoperative Radiation to a Dose of 21 Gy in a Single Fraction.

OR

2. MammoSite® Brachytherapy consisting of a dose of 34 Gy delivered over 10 fractions of 3.4 Gy twice daily over 5 days, with at least 6 hours between fractions.

Eligible patients include:

Patients with a prior ipsilateral breast cancer (invasive, or *in situ*) initially treated with tylectomy and whole breast radiation (with or without tumor bed boost).

Patients who have had at least five years of time elapsed since the end of the prior course of radiation.

Patients with histologically confirmed recurrences comprised of ductal carcinoma in-situ, invasive ductal, medullary, papillary, colloid (mucinous), or tubular histologies.

Patients with histologically confirmed unifocal recurrences measuring  $\leq 3$  cm.

Patients with negative resection margins with at least a 2 mm margin from the invasive and in-situ cancer or a negative re-excision.

Patients with invasive recurrences that have a negative re-staging work-up consisting of at least a CT chest/abdomen and bone scan.

Hormonal therapy is allowed. If chemotherapy is planned, it must begin no earlier than two weeks following completion of radiation.

Patients must be  $\geq 18$  years of age.

Patients with a negative pregnancy test.

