## **2.0 OBJECTIVES**

- 2.1 To determine the in breast recurrence rate following repeat radiation to the breast. These patients will be followed for a period of five years following completion of radiation to determine these rates.
- 2.2 To determine the cosmetic outcome resulting from partial breast re-irradiation using different techniques, including both physician and patient rated scales.
- 2.3 To determine patient satisfaction of partial breast re-irradiation as it pertains to their overall treatment experience as measured by a questionnaire.
- 2.4 To determine if there are patient factors illuminated during a discussion of informed consent, which limit a patient's suitability to receive partial breast re-irradiation delivered by a particular technique.
- 2.5 To evaluate tylectomy wound healing and overall complication rate after partial breast re-irradiation.
- 2.6 To determine ipsilateral breast tumor recurrence rates as well as tumor bed recurrence rates. These patients will be followed for a period of five years following completion of the second course of radiation to determine these rates.

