## APPENDIX II

### Patient Cosmesis/QOL form

Date Questionnaire Completed: \_\_\_\_\_ Patient #: \_\_\_\_\_

My treatment was: (check one)

- ☐ One time radiation treatment during surgery
- ☐ MammoSite radiation after surgery

Circle the number next to the word that best describes the cosmetic result.

1. EXCELLENT: When compared to the untreated breast or the original appearance of the treated breast, there is minimal or no difference in the size or shape of the treated breast. The way the breast feels (its texture) is the same or slightly different. There may be thickening, scar tissue, or fluid accumulation within the breast but not enough to change the appearance.
2. GOOD: There is slight difference in the size or shape of the treated breast as compared to the opposite breast or the appearance of the breast before treatment. There may be some mild reddening or darkening of the breast. The thickening or scar tissue within the breast causes a mild change in its shape or size.
3. FAIR: There is an obvious difference in the shape and size of the treated breast. This change involves  $\frac{1}{4}$  or less of the breast. There can be moderate thickening or scar tissue of the skin and the breast, and there may be obvious color changes.
4. POOR: There is marked change in the appearance of the treated breast involving more than  $\frac{1}{4}$  of the breast tissue. The skin change may be obvious and detract from the appearance. Severe scarring and thickening of the breast, which clearly alters its appearance, may be present. In retrospect, the breast may have been better treated by a mastectomy.

My satisfaction about the treatment and results is:

1. I am totally satisfied with the treatment and results.
2. I am not totally satisfied but would choose the same treatment again.
3. I am not totally satisfied and would choose the standard 5-6 week course of radiation if I had it to do all over again.
4. I am dissatisfied with my treatment.

Before any treatment to your breast, the size and shape of my breasts was:

1. The same on both sides.
2. Larger on the right side.
3. Larger on the left side.

The size of my breasts now is:

1. The same on both sides.
2. Larger on the right side.
3. Larger on the left side.

Signature of person completing the form: \_\_\_\_\_

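### Both cosmesis forms leave the comparator open in women whose breast was already operated on and irradiated, and Section 8 never uses the scheduled pre-irradiation score

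*Combined protocol and SAP*

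**What the plan says.** Objective 2.2 reads: "To determine the cosmetic outcome resulting from partial breast re-irradiation using different techniques, including both physician and patient rated scales". Section 6.2 has the radiation oncologist and the surgeon rate cosmesis on an established scale, and Appendix II gives the patient the same four grades.

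On both forms, Excellent is judged by "When compared to the untreated breast or the original appearance of the treated breast" and requires that "there is minimal or no difference in the size or shape of the treated breast". Good allows a mild difference "as compared to the opposite breast or the appearance of the breast before treatment". Fair and Poor describe the extent of deformity and name no comparator.

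The Schema restricts entry to women "initially treated with tylectomy and whole breast radiation (with or without tumor bed boost", with at least five years since that radiation ended.

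Appendix I and Section 9 call for the form to be completed after the second breast-conserving operation and before re-irradiation, and then repeated during follow-up. The Section 7 calendar also marks a pre-treatment cosmetic and quality-of-life assessment. In Section 8, the only planned analysis that refers to Appendix I is the incidence and degree of fibrosis.

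**The concern.** In a first-treatment trial, the opposite breast, the original appearance and the appearance before treatment would largely coincide as standards. Here they can differ. Original appearance points to a time before the first cancer. Before treatment could mean before the first course or before this one. The opposite breast is a third standard.

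Two things follow. A follow-up category taken by itself carries the effects of the first lumpectomy, the first radiation and the second operation as well as of re-irradiation, so it does not isolate what objective 2.2 asks for. And two physicians and the patient, or one rater at two visits, may grade the same breast differently because the form lets them use different standards. A published good/excellent percentage would then be hard to read as a result of re-irradiation, and differences between physician and patient ratings would be hard to explain.

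**Working it through.** The documents state no rate, threshold or sample size for cosmesis, so there is no plan figure to reproduce. The check is mainly textual, followed by one illustration.

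**1. Comparators by grade (Appendices I and II)**

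| Grade | Comparator named |
|---|---|
| Excellent | untreated breast, or original appearance |
| Good | opposite breast, or appearance before treatment |
| Fair | none |
| Poor | none |

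No instruction on either form, or in Sections 6 to 9, chooses between them or says which course of treatment is meant. Section 3.2.9 excludes other malignancies only within the previous 5 years, so an older, treated cancer of the opposite breast is not ruled out. For such a woman there may be no untreated breast to compare with.

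**2. Is there a baseline?** Yes. Appendix I and Section 9 place it after the second surgery and before re-irradiation, on the same form, and Section 7 has a pre-treatment entry. Section 9 and Appendix I refer only to the physician form, so a patient-rated baseline rests on the Section 7 row alone.

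**3. Is the baseline used?** No. Section 8 specifies no change score, no shift table, no baseline adjustment and no good/excellent percentage.

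**4. Is the baseline the same for both techniques?** Not necessarily. Under Section 5.1.3, intraoperative radiation is given before the tumor bed is closed. When it is given at the lumpectomy, a score after surgery and before radiation cannot exist. Any earlier score is pre-operative, and the change from it includes the second operation. With MammoSite, Section 5.3.1c1 starts brachytherapy 3 to 7 days after implant, so a post-surgery baseline is possible. Section 10 also allows consent after lumpectomy, so baseline timing can vary within a technique.

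**5. What an absolute score adds (illustration)**

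Assumptions, none of them from the documents: a share b is Fair or Poor at baseline and does not improve, and a share r of the remaining women become Fair or Poor.

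- Absolute Fair/Poor share: A = b + (1 − b) × r
- Newly Fair/Poor share: W = (1 − b) × r
- Difference: A − W = b, whatever r is

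With the planned 30 patients (Section 8) and r = 10%, for example b = 20%: A = 0.20 + 0.80 × 0.10 = 0.28, and W = 0.80 × 0.10 = 0.08.

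| b | Absolute, of 30 | New, of 30 | Difference |
|---|---|---|---|
| 0% | 3.0 | 3.0 | 0 |
| 10% | 5.7 | 2.7 | 3 |
| 20% | 8.4 | 2.4 | 6 |
| 30% | 11.1 | 2.1 | 9 |
| 40% | 13.8 | 1.8 | 12 |

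Over b = 10% to 40% and r = 5% to 20%, A runs from 14.5% to 52% and W from 3% to 18%. The scheduled baseline would itself measure b wherever it can be completed on a consistent comparator.

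**6. What using the baseline would not cure.** It does not remove drift if a rater changes comparator between visits. And a woman already Poor at baseline cannot score worse.

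**The case against.** The strongest reply is that the plan already contains the safeguard. Prior damage is recorded on the same form before radiation, so it can be separated from later change. This stands. A reader might infer that the scale charges first-treatment damage to re-irradiation, but the documents do not support that. It is true only of a follow-up score read alone, and the gap is that Section 8 does not say how the baseline will be used.

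Three further inferences are tempting and also fail.

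- **That the wording alone puts raters one to three categories apart, or shifts the good/excellent rate by 8 to 24 points.** The point range comes from assumed entry shares of 10% to 30% and an assumed 80% good/excellent rate independent of entry status: 0.80 − 0.80 × 0.90 = 0.08 and 0.80 − 0.80 × 0.70 = 0.24. It also supposes that everyone uses one comparator or everyone the other. The category spread requires reading original appearance as appearance at study entry, which is not the natural reading. The good/excellent rates of one third and 69% in the re-irradiated series cited in Section 1.0 come from different techniques and doses, with comparators not reported, so they are no evidence either.
- **That the patient item "Before any treatment to your breast, the size and shape of my breasts was" contaminates the cosmesis grade.** It is a separate symmetry question, paired with one on current size, and it records natural asymmetry.
- **That the breast just before treatment should become the comparator.** Every woman would then be Excellent at baseline by definition.

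It is also fair to say that cosmesis is not the primary objective in Section 8, that Section 8 plans no test between techniques, and that technique is chosen by suitability and preference, so any contrast is confounded whatever the wording. Final appearance also matters in its own right when the alternative is mastectomy. These points argue for keeping the absolute score and a descriptive analysis. They do not supply a comparator or a use for the baseline.

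**Conclusion.** The concern holds in limited form. Both forms offer alternative comparators for the two upper grades and none for the two lower ones, in a population where the alternatives can differ. A post-treatment category read alone cannot give the outcome that objective 2.2 attributes to re-irradiation. The data to separate earlier damage are largely scheduled, but Section 8 makes no use of them, and where intraoperative radiation is given at lumpectomy the stated baseline cannot be obtained.

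The size is unknown, because no entry cosmesis figure is given. Under the assumption that women who enter Fair or Poor do not improve, the absolute Fair/Poor rate overstates the new Fair/Poor rate by their entry share b. The documents do not support a claim that the scores are already being misattributed, or any particular shift in percentage points. This affects the interpretation of a descriptive objective that is not the primary one.

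**What to change.** 1. **Forms.** In Appendices I and II, name one comparator for all four grades, used by every rater at every visit. The opposite breast is one option, with a note on the form where that breast has itself been treated. Leave the symmetry item about the breasts before any treatment as it is.
2. **Section 8.** For objective 2.2, report a baseline-to-follow-up shift table and the percentage whose category worsened from the scheduled pre-treatment score, by technique and descriptively, beside the absolute good/excellent percentage. Name the follow-up visits; one and five years appear in both Section 7 and Section 9. Report women already Poor at baseline separately, because they cannot worsen.
3. **Baseline timing.** Record whether the baseline was taken before or after the second excision. Where intraoperative radiation is given at lumpectomy, label the change as second surgery plus re-irradiation, and do not pool it with changes from post-surgery baselines.

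The cost is rewording two forms, one added data field and a short addition to Section 8, using assessments already scheduled. The downsides are a little more analysis and a comparator slightly narrower than the current scale; keeping the absolute percentage preserves a link to the good/excellent rates in Table 1.

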## APPENDIX II

### Patient Cosmesis/QOL form

Date Questionnaire Completed: \_\_\_\_\_ Patient #: \_\_\_\_\_

My treatment was: (check one)

- ☐ One time radiation treatment during surgery
- ☐ MammoSite radiation after surgery

Circle the number next to the word that best describes the cosmetic result.

1. EXCELLENT: When compared to the untreated breast or the original appearance of the treated breast, there is minimal or no difference in the size or shape of the treated breast. The way the breast feels (its texture) is the same or slightly different. There may be thickening, scar tissue, or fluid accumulation within the breast but not enough to change the appearance.
2. GOOD: There is slight difference in the size or shape of the treated breast as compared to the opposite breast or the appearance of the breast before treatment. There may be some mild reddening or darkening of the breast. The thickening or scar tissue within the breast causes a mild change in its shape or size.
3. FAIR: There is an obvious difference in the shape and size of the treated breast. This change involves  $\frac{1}{4}$  or less of the breast. There can be moderate thickening or scar tissue of the skin and the breast, and there may be obvious color changes.
4. POOR: There is marked change in the appearance of the treated breast involving more than  $\frac{1}{4}$  of the breast tissue. The skin change may be obvious and detract from the appearance. Severe scarring and thickening of the breast, which clearly alters its appearance, may be present. In retrospect, the breast may have been better treated by a mastectomy.

My satisfaction about the treatment and results is:

1. I am totally satisfied with the treatment and results.
2. I am not totally satisfied but would choose the same treatment again.
3. I am not totally satisfied and would choose the standard 5-6 week course of radiation if I had it to do all over again.
4. I am dissatisfied with my treatment.

Before any treatment to your breast, the size and shape of my breasts was:

1. The same on both sides.
2. Larger on the right side.
3. Larger on the left side.

The size of my breasts now is:

1. The same on both sides.
2. Larger on the right side.
3. Larger on the left side.

Signature of person completing the form: \_\_\_\_\_

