The term breast conserving therapy (BCT) indicates breast cancer treatment that involves resection of the cancer with a rim of normal tissue, axillary lymph node dissection for those with invasive cancer, and breast radiotherapy. The major advantage of BCT is related to the superior cosmetic result and reduced psychological and emotional trauma resulting from this procedure compared to mastectomy.

Standard therapy after tumor excision generally includes five weeks of external beam XRT to the whole breast (45-50 Gy) followed by a boost to the tumor bed with either an additional 8 to 10 fractions (days) of external beam XRT or a two to three day interstitial implant. The rationale for this approach is based upon two principles. First, higher doses of XRT are given to the 'tumor bed' in an attempt to control residual small foci of cancer that may be left behind after excision alone. Second, whole breast XRT is used to eliminate possible areas of occult multicentric in situ or infiltrating cancer in remote areas of the breast. That such remote, multicentric areas of cancer exist has long been established. However, the biological significance of these areas of occult cancer is unknown and the necessity to prophylactically treat the entire breast has recently been questioned. For instance, there are now at least five prospective randomized trials that have been

conducted comparing the outcome of patients treated with excisional biopsy alone or followed by whole breast XRT (5,13-17). In all of these trials, the majority of recurrences in the breast of patients who did not receive XRT occurred at or in the area of the tumor bed. Thus, it would appear that XRT after tumor excision exerts its maximal effect upon reducing breast cancer recurrence at or near the tumor site (17).

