### **Current Trial Design**

Patients enrolled in this protocol will be selected to insure that their cancers have been adequately excised and that tumor bed irradiation alone will be feasible. Depending on individual patient characteristics (for example, proximity of the tumor cavity to the skin,

patient's ability to tolerate another surgical procedure) a decision will be made jointly by the breast surgeon, radiation oncologist and medical oncologist at our multi-disciplinary conference as to which method of partial breast irradiation is best suited for the patient. Practical considerations will also be taken into account, in the decision of which type of radiation to offer—that said, provided a patient is medically eligible for either type of radiation, she will be given the opportunity to decide which treatment she would like. Some patients may not be deemed medically fit to undergo another surgical procedure, and might then be offered MammoSite based APBI, because the catheter does not necessarily have to be placed in the operating room. Another example in which one therapy might be more advisable than another, is a woman who has a history of immune deficiency and resultant life threatening infections—rather than leaving a MammoSite catheter with an open wound for more than one week, one might opt for a single treatment in the operating room at the time of lumpectomy. One endpoint of the study will be to evaluate which patients are best suited for treatment by each of the available partial breast irradiation options.

The aim of the study will be to evaluate patient acceptance of the concept of partial breast re-irradiation for an IBTR, in the hope that there will be an alternative treatment to the recognized standard of care (mastectomy). We will also evaluate cosmetic outcome following the procedure. Long term outcome data regarding further in-breast recurrences as well as tumor bed recurrence will also be recorded and analyzed.

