### **6.0 MEASUREMENT OF EFFECT**

The endpoints of this study are as follows:

- 6.1 Determination ipsilateral breast tumor recurrence rates as well as tumor bed recurrence rates. The breast quadrant of recurrence will be recorded. Patients will be followed for a period of five years following completion of radiation.
- 6.2 Cosmetic outcome as determined by an established scale employed by the radiation oncologist and the surgeon.
- 6.3 Patient satisfaction with the procedure as determined by a questionnaire to be completed by the patients.
- 6.4 Wound healing and overall complication rate after partial breast re-irradiation.
- 6.5 Determination of which patients are best suited for each individual technique of performing partial breast irradiation. Measurement of this will be observational.

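### Option 3 of the Appendix II satisfaction item names a first-line alternative (multi-week radiation), so answers to it cannot be interpreted and a hindsight preference for mastectomy is not identified

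*Combined protocol and SAP*

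**What the plan says.** Section 1.0, Current Trial Design, gives the purpose in narrative form: "The aim of the study will be to evaluate patient acceptance of the concept of partial breast re-irradiation for an IBTR". It adds that the investigators would like this to become "an alternative treatment to the recognized standard of care (mastectomy"). The numbered objective is narrower. Objective 2.3 reads "To determine patient satisfaction of partial breast re-irradiation as it pertains to their overall treatment experience as measured by a questionnaire", and endpoint 6.3 reads "Patient satisfaction with the procedure as determined by a questionnaire to be completed by the patients".

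Appendix II is the only patient questionnaire among the appendices in the table of contents. Its satisfaction item offers four answers:

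1. Complete satisfaction.
2. Less than complete satisfaction, but she would have the same treatment again.
3. Less than complete satisfaction, and she "would choose the standard 5-6 week course of radiation if I had it to do all over again".
4. Dissatisfaction, with no alternative named.

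The Schema describes the eligible women as having a prior cancer "initially treated with tylectomy and whole breast radiation (with or without tumor bed boost"). Section 7.0 schedules the cosmetic and quality-of-life assessment before treatment, one month after radiation, every three months for one year, and at five years. Section 8.0 plans no analysis of the satisfaction item.

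**The concern.** Option 3 asks a less-than-satisfied woman which treatment she would rather have had, and it supplies one answer. In a first-line partial-breast trial that answer would be natural, because the alternative to partial breast treatment would be a full course of whole breast radiation. Here the patients have a recurrence after such a course, and the protocol presents mastectomy as the treatment they would otherwise receive.

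Two things are at stake. An answer recorded under option 3 cannot be given a definite meaning. And the completed forms cannot show how many women would, looking back, have preferred mastectomy. That number bears on the acceptance aim, and it cannot be recovered later from the forms.

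**Working it through.** The documents give no figure to reproduce here, so the check is a comparison of texts followed by a mapping of the answers.

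**What the multi-week course is in this protocol.** Section 1.0 describes "five weeks of external beam XRT to the whole breast (45-50 Gy"), followed by a tumor bed boost, as the usual treatment after tumor excision. That is the first-line setting. In the discussion of recurrence, the same section explains salvage mastectomy partly by the tissue damage that irradiating the breast again could cause. Nowhere is a 5-6 week course called standard for a recurrence. It is not a study treatment either: the Schema and Section 5.0 list only single-dose intraoperative radiation and MammoSite brachytherapy.

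**What a tick at option 3 could mean.** At least three readings fit the words:
- she would want whole breast radiation now, for the recurrence;
- she is thinking back to her first cancer, for which she has already had whole breast radiation;
- she would rather have had whatever is standard, and this is the only standard treatment offered.

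Nothing on the form separates these readings.

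**Where a preference for mastectomy would go.**
- Option 1 does not fit a woman who regrets the treatment.
- Option 2 contradicts her view, because it commits her to the same treatment again.
- Option 3 names a different treatment.
- Option 4 records dissatisfaction without saying what she would have preferred.

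She must therefore use option 3 or option 4. The form mentions mastectomy once, inside the description of a poor cosmetic result. That line rates appearance and does not ask for a choice.

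**What can be estimated.** Let *n* women complete the form (at most 30), with *a* at option 3 and *b* at option 4. Assume that nobody who ticks option 1 or 2 would have preferred mastectomy. Then:
- proportion satisfied or willing to repeat = (*n* − *a* − *b*)/*n*, which the present form gives directly;
- proportion preferring mastectomy lies between 0 and (*a* + *b*)/*n*, and the form cannot narrow that range.

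The documents give no basis for predicting *a* or *b*, so the width of the range cannot be stated in advance.

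**The case against.** The best case for leaving the form alone has four parts.

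*The form does what the numbered objective asks.* Objective 2.3 and endpoint 6.3 concern satisfaction, not preference against mastectomy. Acceptance appears only in the narrative, which neither defines it as a hindsight choice between treatments nor ties it to this form. This stands, and it limits the point. A reader might infer that a patient-acceptance endpoint has been made unmeasurable. The documents contain no numbered endpoint of that kind, and options 1, 2 and 4 still serve the satisfaction endpoint.

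*External beam re-treatment exists.* Section 1.0 cites a series treated with electrons to the excision cavity and another in which some patients had whole breast radiation again with a brachytherapy boost. Option 3 might be meant for such courses. This does not stand: the protocol calls neither standard for a recurrence and describes the supporting literature as very limited.

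*Mastectomy is not a choice for everyone.* Section 1.0 foresees women who decline it and women who cannot have it. This stands as an argument about the remedy. Simply putting mastectomy into option 3 would ignore women for whom it was not available. It would also overlap option 4, since a dissatisfied woman who would prefer mastectomy could tick either. It does not justify the radiation wording.

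*The main analyses do not depend on this item.* This stands. The stopping rules, the recurrence estimate and the safety summaries in Section 8.0 do not use it.

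**Conclusion.** The point holds in a limited form. Option 3 names an alternative that belongs to first-line breast conservation, so answers to it cannot be interpreted. A hindsight preference for mastectomy is not identified, because it would be mixed into options 3 and 4.

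One of the four answers is defective, and at most 30 women are affected. How many would choose it is unknown. The conclusion rests on the plain meaning of the four answers and on Appendix II being the only patient questionnaire.

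A reader might also infer that mastectomy regret would be scattered across option 2 as well. The wording does not support that, because option 2 states willingness to have the same treatment again. Nor do the documents support saying that satisfaction goes unmeasured. The change is worth making because it is cheap and serves the stated aim, but no safety or recurrence result is in doubt.

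**What to change.** Remove the 5-6 week radiation wording from option 3, so that the satisfaction item measures satisfaction only. Add a separate preference item along these lines: *If I had it to do over again I would choose: the same treatment / mastectomy / other or unsure / mastectomy was not an option for me.* A separate item avoids the overlap with option 4, and the last answer allows for women who could not have had mastectomy.

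In Section 8.0, state that two proportions will be reported with exact 95% confidence intervals:
- women choosing satisfaction option 1 or 2;
- women preferring mastectomy, among those for whom it was an option.

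Report both at the 1-year and 5-year assessments already in Section 7.0, so no visit is added. With at most 30 women, and fewer in the second denominator, these proportions are descriptive.

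The cost is a small form revision and an IRB submission. Forms already completed on the existing version would not be comparable on this item and should be reported separately. The change concerns measurement only and leaves treatment and clinical management as they are.
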